#### 3.2 Secondary Objectives

- The first key secondary objective is to assess whether latency delay at 180 days decreases to a greater extent in Group A (exposed to BZA for 90 days during both Stage 1 and Stage 2) when compared to Group B (exposed to placebo during Stage 1 and BZA for only 90 days during Stage 2).
- The second key secondary objective is to demonstrate the tolerability of BZA in this population. This will include special focus with regards to fatigue as this is a major symptom for patients suffering from multiple sclerosis.
- The third key secondary objective is to document the safety of BZA in this population of patients.
- The fourth key secondary objective of this study is to help assess which secondary and tertiary outcomes are likely to be informative for future remyelinating trials in multiple sclerosis.

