### 4 STUDY DESIGN

#### 4.1 Study Overview

This is a 6-month randomized, single center, double blinded, delayed start study in 50 patients with relapsing remitting multiple sclerosis and identified injury to the anterior visual pathway.

Patients will be randomized 1:1 into two groups: Group A and Group B. Group A will receive 180 days of Bazedoxifene while Group B will receive 90 days of placebo followed by 90 days of Bazedoxifene. Patients will receive two fixed oral tablets of 20mg Bazedoxifene (Conbriza) daily (to be taken at the same time). Patients will be permitted to remain on their standard disease modifying treatment during the course of the study.

Screening data will be reviewed to determine subject eligibility. Subjects who meet all inclusion criteria and none of the exclusion criteria will be entered into the study

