## 8 STUDY TREATMENTS

### 8.1 Method of Assigning Subjects to Treatment Groups

Up to 50 eligible patients will be randomly assigned to 'Early' or 'Delayed Start' treatment groups in a 1:1 ratio using a SAS-based computer-generated randomization scheme developed by the study data management provider. The CTSI statistician advising the PI will complete a randomization worksheet.

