## 8.2 Blinding

Due to the objectives of the study, the identity of test and control treatments will not be known to investigators, research staff, or patients. The following study procedures will be in place to ensure double-blind administration of study treatments.

- Access to the randomization code will be strictly controlled.
- The CTSI statistician advising the PI will perform the randomization/blinding chart and provide this to the Compounding Pharmacy. They will perform interim safety analysis without unblinding the study, and will only unblind the study to the investigators at the end of study.
- Packaging and labeling of test and control treatments will be identical to maintain the blind.
- Packaging and labeling will be done by pharmacy personnel who are not involved in analysis of study data.

The study blind will be broken on completion of the clinical study and after the study database has been locked. The investigators will be given the randomization worksheet from the CTSI statistician after the last participant has completed their study.

During the study, the blind may be broken **only** in emergencies when knowledge of the patient's treatment group is necessary for further patient management. When possible, the Investigator should discuss the emergency with [name] prior to unblinding.

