## **12 DISCONTINUATION AND REPLACEMENT OF SUBJECTS**

### **12.1 Early Discontinuation of Study Drug**

A subject may be discontinued from study treatment at any time if the subject, the investigator, or the Sponsor feels that it is not in the subject's best interest to continue. The following is a list of possible reasons for study treatment discontinuation:

- Subject withdrawal of consent (or assent)
- Subject is not compliant with study procedures
- Adverse event that in the opinion of the investigator would be in the best interest of the subject to discontinue study treatment
- Protocol violation requiring discontinuation of study treatment
- Lost to follow-up
- Sponsor request for early termination of study
- Positive pregnancy test (females)

If a subject is withdrawn from treatment due to an adverse event, the subject will be followed and treated by the Investigator until the abnormal parameter or symptom has resolved or stabilized.

All subjects who discontinue study treatment should come in for an early discontinuation visit as soon as possible and then should be encouraged to complete all remaining scheduled visits and procedures.

All subjects are free to withdraw from participation at any time, for any reason, specified or unspecified, and without prejudice.

Reasonable attempts will be made by the investigator to provide a reason for subject withdrawals. The reason for the subject's withdrawal from the study will be specified in the subject's source documents. Refer to Section 10 for early termination procedures.

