## 15 STATISTICAL METHODS AND CONSIDERATIONS

Prior to the analysis of the final study data, a detailed Statistical Analysis Plan (SAP) will be written describing all analyses that will be performed. The SAP will contain any modifications to the analysis plan described below.

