### 15.4 Analysis of Secondary Endpoints

Secondary endpoints will be analyzed using the same methods as primary endpoints.

Safety and tolerability data will be summarized by treatment group.

Adverse event rates will be coded by body system and MedDra classification term. Adverse events will be tabulated by treatment group and will include the number of patients for whom the event occurred, the rate of occurrence, and the severity and relationship to study drug.

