### 15.5 Interim Analysis

After each patient completes the Week 6 phone call, the side effects reported will be analyzed.

When 50% of patients have completed the study through Study Visit 2 (total visit 3), an interim analysis for safety will be conducted by the PI.

Serious adverse events will be monitored by the committee on an ongoing basis throughout the study.

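### Section 15.4 tabulates adverse events by randomised group with no period stated; read naturally as whole-study, half of the comparator's patient-time is on BZA

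*Combined protocol and SAP*

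**What the plan says.** All references are to the combined protocol and SAP.

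- Section 15.4, on safety: "Adverse events will be tabulated by treatment group and will include the number of patients for whom the event occurred". It also asks for rate, severity and relationship to study drug. It names no stage, Day 90 cut, drug at onset or exposure denominator.
- Section 8.1 uses the same term for the randomised arms: patients "will be randomly assigned to 'Early' or 'Delayed Start' treatment groups in a 1:1 ratio".
- Section 4.1: Group A takes BZA for 180 days, and "Group B will receive 90 days of placebo followed by 90 days of Bazedoxifene".
- Section 9.1.7 has adverse events captured for the whole study, with start and stop dates. Section 15.1 defines the Safety Population by randomisation and one dose, and gives no rule for assigning an event to a period or a drug.
- Section 3.2: tolerability is the second key secondary objective, and "The third key secondary objective is to document the safety of BZA in this population of patients".
- Section 3.1, by contrast, does state a window for the primary efficacy comparison: the first 90 days in each group.
- Section 15 promises a SAP before the final analysis: "The SAP will contain any modifications to the analysis plan described below".

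**The concern.** The design gives one period in which the two groups differ as BZA versus placebo: Stage 1, the first 90 days. The plan uses that window for efficacy but does not carry it into the adverse-event table. If events are cumulated over the whole study by randomised group, those that Group B has on BZA after Day 90 are counted in the column a reader would take as the comparator.

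The result would be hard to interpret. Similar rates in the two columns could mean that BZA adds no events, or that both columns contain BZA exposure; the table alone would not show which. This is the only between-group comparison of adverse events that the documents state. Section 14 plans no data and safety monitoring board, and neither the interim safety analysis nor the Week 6 review is described as a comparison by arm.

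**Working it through.** **The plan's own figure.** Section 15.4 contains none to reproduce. The 90% power in Section 15.6 concerns P100 latency and plays no part here.

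**Exposure.** Inputs: 25 per group (Section 15.6), 90 + 90 days (Section 4.1), full follow-up assumed.

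- Group A: 25 × 180 = 4,500 BZA patient-days.
- Group B: 25 × 90 = 2,250 placebo and 2,250 BZA patient-days.
- BZA share of Group B's time: 2,250 / 4,500 = 50%.
- Share of all BZA time that sits in Group B's column: 2,250 / 6,750 = 33%.

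No event rate is needed for this part.

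**Effect on the table.** The documents give no event rates for this population, so the risks are assumed. Let p0 and p1 be the 90-day risks on placebo and BZA, constant and independent between periods, and count patients who ever had the event.

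- Stage 1: A = p1, B = p0, excess = 25(p1 − p0).
- Whole study: A = 1 − (1 − p1)², B = 1 − (1 − p0)(1 − p1), so A − B = (p1 − p0)(1 − p1).
- No visible excess: the probability that Group A's count is no higher than Group B's (ties included), from two independent binomials with n = 25.

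| p0 / p1 | Stage 1 ratio; excess patients | Whole-study A vs B | Whole-study ratio; excess patients | No visible excess: Stage 1 → whole study |
|---|---|---|---|---|
| 5% / 10% | 2.0; 1.25 | 19% vs 14.5% | 1.31; 1.1 | 0.345 → 0.406 |
| 10% / 15% | 1.5; 1.25 | 27.8% vs 23.5% | 1.18; 1.1 | 0.374 → 0.427 |
| 10% / 20% | 2.0; 2.5 | 36% vs 28% | 1.29; 2.0 | 0.210 → 0.323 |
| 10% / 30% | 3.0; 5.0 | 51% vs 37% | 1.38; 3.5 | 0.049 → 0.194 |
| 20% / 40% | 2.0; 5.0 | 64% vs 52% | 1.23; 3.0 | 0.078 → 0.235 |

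The loss in excess patients runs from 1.25 − 1.125 ≈ 0.1 to 5.0 − 3.0 = 2.0.

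**Departures from constant risk** (p0 = 10%, p1 = 20%, equal retention and ascertainment):

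- Excess only in the first 90 days of exposure: A = 1 − 0.8 × 0.9 = 28%; B = 1 − 0.9 × 0.8 = 28%. The whole-study table shows nothing.
- Excess only after 90 days of BZA: A = 1 − 0.9 × 0.8 = 28%; B = 1 − 0.9² = 19%. Stage 1 shows 10% vs 10%, so here only the whole-study table is informative.
- No BZA effect: both ratios are 1.00.

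**Precision of a Stage 1 table** at 20% vs 10%: half-width 1.96 × √(0.2 × 0.8/25 + 0.1 × 0.9/25) = 0.196, about ±20 percentage points. Exact Fisher power (two-sided 0.05) is 0.086 in Stage 1, and 0.051 for the whole-study 36% vs 28%.

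**The case against.** **The text is silent, not wrong, and a detailed SAP is to follow.** It is true that Section 15.4 never says whole study, and a reader who infers an express rule to pool both stages goes further than the words do. But groups defined by randomisation, events captured throughout and no split anywhere make the whole-study table the natural result of following the text. The SAP could add a split, but it is described as modifying this plan.

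**Other looks cover Stage 1.** Section 15.5 sets a mid-study safety look: "When 50% of patients have completed the study through Study Visit 2 (total visit 3), an interim analysis for safety". Section 8.2 says of the statistician: "They will perform interim safety analysis without unblinding the study" (Section 15.5 gives the task to the PI instead). That wording does not exclude a table by coded arm, and Week 6 falls wholly within Stage 1. Adverse events are also inventoried at each visit, so Visit 3 data could give a Stage 1 table. What stands is that the data would allow it. What does not follow is that it is planned: no table by arm is stated for either look, the interim covers about half the patients, and Week 6 covers only part of Stage 1.

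**The safety objectives are not comparative, and the numbers are small.** Section 3.2 speaks of documenting safety and demonstrating tolerability, without reference to placebo. The loss in patient counts is modest and rests on assumed rates. At 15% vs 10% and 10% vs 5%, even a Stage 1 table shows no excess in roughly a third or more of trials. All of this stands and limits the weight of the point. Still, Section 15.4 itself plans a table by group, and low precision is no reason to mix exposures in it.

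**Existing records do not support every refinement.** This also stands. Sections 9.1.7 and 11.1 list start and stop dates and a severity, but no date of a severity change. Section 8.6 records quantities dispensed and returned. Section 8.4.2 allows short supplies with re-supply by mail, and Appendix 1 counts returned drug only at Month 6. Dispensing entries therefore do not fix the first Stage 2 dose; only the diary (Section 8.7) dates it.

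**Conclusion.** The point holds as a gap in Section 15.4 that, followed naturally, gives a diluted safety comparison; it should be repaired. That half of Group B's time is on BZA follows from the design, assuming full follow-up. The size of the dilution does not: it depends on assumed risks. Under constant risk, ratios of 1.5 to 3.0 fall to between 1.18 and 1.38, while the excess shrinks by only about 0.1 to 2.0 patients per 25.

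Three stronger conclusions might be inferred, and the documents support none of them.

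- That information is lost. It is not: event start dates and diary dosing dates are to be collected, so the split can be derived.
- That all safety data are affected. The problem is cumulative event counts. MFIS at Month 3, if summarised by visit, already compares BZA with placebo, though Section 15.4 does not state that layout either.
- That the whole-study table is useless, or that a Stage 1 table would settle safety. Harm that begins after 90 days of BZA appears only in the former, and the latter has about 9% power at 20% vs 10%.

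**What to change.** Amend Section 15.4, before the SAP is written, as follows.

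(a) Make the main comparative adverse-event table Stage 1 only, Group A versus Group B by randomised group. Count events with onset from first dose to first Stage 2 dose as dated in the diary. Where the diary does not give that date, use the Visit 3 date, or Day 90 or last contact if there is no Visit 3. Events after an early stop stay in the randomised group; Section 12.1 supports this, since such patients "should be encouraged to complete all remaining scheduled visits and procedures".

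(b) Add a descriptive table by treatment at onset (placebo or BZA) with patient-days for each, using recorded event start dates. Add no separate rule for worsening after the switch unless the case report form records the dates of severity changes.

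(c) Keep the whole-study table by group, labelled early versus delayed start rather than BZA versus placebo, because Stage 1 cannot show harm that begins after 90 days of BZA.

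The cost is a few extra tables and a short attribution rule, with no new visits. The drawbacks are reliance on a self-kept diary for the switch date and a Stage 1 table too imprecise (about ±20 percentage points at 20% vs 10%) to be more than descriptive.

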### 15.5 Interim Analysis

After each patient completes the Week 6 phone call, the side effects reported will be analyzed.

When 50% of patients have completed the study through Study Visit 2 (total visit 3), an interim analysis for safety will be conducted by the PI.

Serious adverse events will be monitored by the committee on an ongoing basis throughout the study.

### 15.6 Sample Size and Randomization

With 25 patients per group, the study has 90% power to detect a 50% relative reduction in latency with BZA compared to placebo at the 3-month outcome for group 1 assuming a two-sided test with alpha = 0.05. Study size may be expanded to compensate for dropouts over the short study period. To maximize study efficiency and resource utilization these subjects will not be enrolled unless necessary.

## 16 DATA COLLECTION, RETENTION AND MONITORING

### 16.1 Data Collection Instruments

The Investigator will prepare and maintain adequate and accurate source documents designed to record all observations and other pertinent data for each subject treated with the study drug.

Study personnel at each site will enter data from source documents corresponding to a subject's visit into the protocol-specific electronic Case Report Form (eCRF) when the information corresponding to that visit is available. Subjects will not be identified by name in the study database or on any study documents to be collected by the Sponsor (or designee), but will be identified by a site number, subject number and initials.

If a correction is required for an eCRF, the time and date stamps track the person entering or updating eCRF data and creates an electronic audit trail.

The Investigator is responsible for all information collected on subjects enrolled in this study. All data collected during the course of this study must be reviewed and verified for completeness and accuracy by the Investigator. A copy of the CRF will remain at the Investigator's site at the completion of the study.

### 16.2 Data Management Procedures

The data will be entered into a validated database. The Data Management group will be responsible for data processing, in accordance with procedural documentation. Database lock will occur once quality assurance procedures have been completed.

All procedures for the handling and analysis of data will be conducted using good computing practices meeting FDA guidelines for the handling and analysis of data for clinical trials.

### 16.3 Data Quality Control and Reporting

After data have been entered into the study database, a system of computerized data validation checks will be implemented and applied to the database on a regular basis. Queries are entered, tracked, and resolved through the EDC system directly. The study database will be updated in accordance with the resolved queries. All changes to the study database will be documented.

### 16.4 Archival of Data

The database is safeguarded against unauthorized access by established security procedures; appropriate backup copies of the database and related software files will be maintained. Databases are backed up by the database administrator in conjunction with any updates or changes to the database.

At critical junctures of the protocol (e.g., production of interim reports and final reports), data for analysis is locked and cleaned per established procedures.

### 16.5 Availability and Retention of Investigational Records

The Investigator must make study data accessible to the monitor, other authorized representatives of the Sponsor (or designee), IRB/IEC, and Regulatory Agency (e.g., FDA) inspectors upon request. A file for each subject must be maintained that includes the signed Informed Consent, HIPAA Authorization and Assent Form and copies of all source documentation related to that subject. The Investigator must ensure the reliability and availability of source documents from which the information on the CRF was derived.

All study documents (patient files, signed informed consent forms, copies of CRFs, Study File Notebook, etc.) must be kept secured for a period of two years following marketing of the investigational product or for two years after centers have been notified that the IND has been discontinued. There may be other circumstances for which the Sponsor is required to maintain study records and, therefore, the Sponsor should be contacted prior to removing study records for any reason.

## 16.6 Monitoring

Monitoring visits will be conducted by representatives of the Sponsor according to the U.S. CFR Title 21 Parts 50, 56, and 312 and ICH Guidelines for GCP (E6). By signing this protocol, the Investigator grants permission to the Sponsor (or designee), and appropriate regulatory authorities to conduct on-site monitoring and/or auditing of all appropriate study documentation.

## 16.7 Subject Confidentiality

In order to maintain subject confidentiality, only a subject number and subject initials will identify all study subjects on CRFs and other documentation submitted to the Sponsor. Additional subject confidentiality issues (if applicable) are covered in the Clinical Study Agreement.

# 17 ADMINISTRATIVE, ETHICAL, REGULATORY CONSIDERATIONS

The study will be conducted according to the Declaration of Helsinki, Protection of Human Volunteers (21 CFR 50), Institutional Review Boards (21 CFR 56), and Obligations of Clinical Investigators (21 CFR 312).

To maintain confidentiality, all laboratory specimens, evaluation forms, reports and other records will be identified by a coded number and initials only. All study records will be kept in a locked file cabinet and code sheets linking a patient's name to a patient identification number will be stored separately in another locked file cabinet. Clinical information will not be released without written permission of the subject, except as necessary for monitoring by the FDA. The Investigator must also comply with all applicable privacy regulations (e.g., Health Insurance Portability and Accountability Act of 1996, EU Data Protection Directive 95/46/EC).

## 17.1 Protocol Amendments

Any amendment to the protocol will be written by PI. Protocol amendments cannot be implemented without prior written IRB/IEC approval except as necessary to eliminate immediate safety hazards to patients. A protocol amendment intended to eliminate an apparent immediate hazard to patients may be implemented immediately, provided the IRBs are notified within five working days.

## 17.2 Institutional Review Boards and Independent Ethics Committees

The protocol and consent form will be reviewed and approved by the IRB/IEC prior to study initiation. Serious adverse experiences regardless of causality will be reported to the IRB/IEC in accordance with the standard operating procedures and policies of the IRB/IEC, and the Investigator will keep the IRB/IEC informed as to the progress of the study. The Investigator will obtain assurance of IRB/IEC compliance with regulations.

Any documents that the IRB/IEC may need to fulfill its responsibilities (such as protocol, protocol amendments, Investigator's Brochure, consent forms, information concerning patient recruitment, payment or compensation procedures, or other pertinent information) will be submitted to the IRB/IEC. The IRB/IECs written unconditional approval of the study protocol and the informed

consent form will be in the possession of the Investigator before the study is initiated. This approval must refer to the study by exact protocol title and number and should identify the documents reviewed and the date of review.

Protocol and/or informed consent modifications or changes may not be initiated without prior written IRB/IEC approval except when necessary to eliminate immediate hazards to the patients or when the change(s) involves only logistical or administrative aspects of the study. Such modifications will be submitted to the IRB/IEC and written verification that the modification was submitted and subsequently approved should be obtained.

The IRB/IEC must be informed of revisions to other documents originally submitted for review; serious and/or unexpected adverse experiences occurring during the study in accordance with the standard operating procedures and policies of the IRB; new information that may affect adversely the safety of the patients of the conduct of the study; an annual update and/or request for re-approval; and when the study has been completed.

